## **14.6 Record Retention**

Investigators must retain all study records required by the sponsor and applicable ICH-GCP, FDA regulations in a secure and safe facility. The Investigator must consult a representative of the sponsor before disposal of any study records. “Essential documents” are defined as documents that individually and collectively permit evaluation of the conduct of a trial and the quality of the data produced. These documents will be filed according to ICH-GCP regulations in the ISF. It is the responsibility of the sponsor to inform the investigator or institution when these documents no longer need to be retained. Medical records will be maintained according to the James J Peters VA medical center’s requirements. Research Investigator files at JJP VAMC will be destroyed six years after the end of the fiscal year when the research project has been completed per Records Schedule DAA-0015-2015-0004-0032.

## **14.7 Publication Policy**

The sponsor recognizes the importance of communicating medical research and scientific data and their obligations to participants enrolled in a study and therefore, encourage publication of such material in reputable scientific journals and at professional and/or academic seminars or conferences. For multi-center studies, it is intended that the first publication of the study’s primary clinical data be co-authored by designated participating centers and the sponsor or designated representatives. Inclusion of Clinical Investigators in the authorship of any multi-center publication will be based upon substantial contribution to the design, analysis, interpretation of data, drafting and/or critically revising any manuscript(s) derived from the Study. All publications will follow ICMJE Recommendations for the Conduct, Reporting, Editing, and Publication of Scholarly Work in Medical Journals, unless other guidelines are required by the journal. It is understood by the Clinical Investigators that the information generated in this study will be used by the sponsor in connection with the development of the IMP and therefore may be disclosed to government agencies in various countries. To allow for the use of information derived from the study, it is understood that the investigators are obliged to provide the sponsor with complete test results, all study data, and access to all study records. It is mandatory that all data analysis is done on the official monitored sponsor database and that the analysis plan is agreed upon with the sponsor statistician.

Any results of medical investigations with the sponsor and/or publication/lecture/manuscripts based thereon shall be exchanged and discussed by the investigator and sponsor prior to submission for publication or presentation. Due regard shall be given to the sponsor's legitimate interests, e.g., manuscript authorship, obtaining optimal patient protection, coordinating, and maintaining submissions to health authorities, and coordinating with other ongoing studies in the same field. The full details of the processes of producing and reviewing reports, manuscripts, and presentations based on the data from this trial will be described in the Clinical Trial Agreement.

1.0 Introduction

This document contains a Statistical Analysis Plan (SAP) for MPVA6 “A Phase 2, Open-Label, Randomized Comparative Effectiveness Study for MDMA-Assisted Therapy in U.S. Veterans with Chronic PTSD.”

This open-label comparative effectiveness study was designed to explore the relative effectiveness of two vs. three randomly assigned active drug sessions in a sample of U.S. military veterans with at least moderate chronic PTSD. The Primary Outcome measure, the Clinician Administered PTSD Scale (CAPS-5), evaluates changes in PTSD symptom severity and is assessed by a blinded centralized Independent Rater (IR) pool.

Due to various administrative and non-safety related reasons, in May of 2023 MPBC decided to terminate this study with enrollment of approximately twenty participants. Since the new sample size will not support efficacy conclusions, the focus of the analyses described herein has shifted from safety and efficacy to safety only. Sections 2 through 6 state the study objectives, study measures, design, randomization, and sample size/power as described in the Protocol. Section 7, analysis, has been modified to reflect the changes resulting from early termination of the study.

2.0 Study Objectives

2.1 Primary Objective

The primary objective of this study is to compare the effectiveness of two versus three sessions of MDMA-assisted therapy in treatment of PTSD, based on mean change in CAPS-5 Total Severity Score from T1 (Baseline) to T2 (Primary Outcome).

2.2 Secondary Objective

The key secondary objective of this study is to compare the effectiveness of two versus three sessions of MDMA-assisted therapy in clinician-rated functional impairment, as measured by the mean change in Sheehan Disability Scale (SDS) item score from Baseline to T2 (Primary Outcome).

2.3 Safety Objectives

The overall safety objective is to assess severity, incidence and frequency of AEs, AEs of Special Interest (AESIs), and Serious Adverse Events (SAEs), concomitant medication use, and vital signs to support the package insert for MDMA-assisted therapy. The following safety objectives will evaluate the safety of MDMA-assisted therapy:

1. Assess incidence of AEs during Experimental Sessions that may be indicative of a medical complication of the Investigational Medicinal Product (IMP), such as clinical signs and symptoms of chest pain, shortness of breath, or neurological symptoms or any other signs or symptoms that prompt additional vital sign measurements.
2. Assess incidence of AEs by severity
3. Assess incidence of Treatment Emergent AEs (TEAEs) by severity.
4. Assess incidence of TEAEs by severity taken during an Experimental Session and through 2 days after IMP administration.
5. Assess incidence of AESIs, defined as AEs specified in the protocol related to cardiac function and abuse liability.

6. Assess incidence of AEs by severity categorized as leading to discontinuation of IMP, resulting in death or hospitalization, and continuing at Study Termination.
7. Assess incidence of SAEs.
8. Assess incidence of psychiatric concomitant medications taken during an Experimental Session and through 2 days after IMP administration.
9. Assess incidence of any psychiatric concomitant medications taken during the Treatment Period.
10. Assess incidence of serious suicidal ideation and positive suicidal behavior assessed with the Columbia Suicide Severity Rating Scale (C-SSRS).
11. Assess mean changes in blood pressure, heart rate, and body temperature from pre-IMP administration to end of each Experimental Session.

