### 1.2.2 MDMA

MDMA is a ring-substituted phenylisopropylamine derivative invented by the Merck pharmaceutical company in 1912 [24, 25]. Similar to SSRIs, MDMA binds to the serotonin transporter, but has additional effects on carrier-mediated release and reuptake inhibition of serotonin and to a lesser extent in humans, norepinephrine and dopamine [26-32]. MDMA also increases levels of affiliative neurohormones oxytocin and vasopressin, which is hypothesized to increase trust and attenuate reactivity to threatening cues. Some researchers have suggested a role for oxytocin in treating PTSD. The indirect effects of MDMA on central and peripheral neurohormone levels contribute to a novel mechanism that may help regulate the HPA axis during therapy.

Onset of MDMA effects occurs ~0.5 to 1 hour after oral administration, and peak effects occur 1.25 to two hours after the initial dose. Effects of the initial dose last 3 to 6 hours, which is extended to 5 to 8 hours with a supplemental dose administered 1.5 to 2 hours post initial dose. Orally administered doses of MDMA have a half-life of 7 to 9 hours in humans. Unlike approved PTSD medications, therapeutic effects of MDMA have a rapid-onset and do not require daily dosing or a steady state in the blood to be effective. Thus, the effects of MDMA are distinct from and go well beyond anxiolytics and SSRIs. Furthermore, there is no evidence that MDMA creates a physical dependency, as benzodiazepines do. Previous studies of polydrug users have found a small percentage of people exhibit problematic use of Ecstasy (material represented as containing MDMA) [33, 34]. Studies of regular or problematic Ecstasy users indicate that on average, regular use occurs no more often than once a week [35]. Hence, MDMA may have moderate abuse potential. See the Investigator's Brochure (IB) for a more detailed explanation.

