## 2.4 Safety Objectives

The overall safety objective is to assess severity, incidence and frequency of AEs, AEs of Special Interest (AESIs), and Serious Adverse Events (SAEs), concomitant medication use, and vital signs to support the package insert for MDMA-assisted therapy. The following safety objectives will evaluate the safety of MDMA-assisted therapy:

1. Assess incidence of AEs during Experimental Sessions that may be indicative of a medical complication of the Investigational Product (IP), such as clinical signs and symptoms of chest pain, shortness of breath, or neurological symptoms or any other signs or symptoms that prompt additional vital sign measurements.
2. Assess incidence of AEs by severity.
3. Assess incidence of Treatment Emergent AEs (TEAEs) by severity.
4. Assess incidence of TEAEs by severity taken during an Experimental Session and through 2 days after IP administration.
5. Assess incidence of AESIs, defined as AEs specified in the protocol related to cardiac function and abuse liability.
6. Assess incidence of AEs by severity categorized as leading to discontinuation of IP, resulting in death or hospitalization, and continuing at Study Termination.
7. Assess incidence of SAEs.
8. Assess incidence of concomitant medications of interest taken during an Experimental Session and through 2 days after IP administration.
9. Assess incidence of any psychiatric concomitant medications taken during the Treatment Period.
10. Assess incidence of serious suicidal ideation and positive suicidal behavior assessed with the Columbia Suicide Severity Rating Scale (C-SSRS).
11. Assess mean changes in blood pressure, heart rate, and body temperature from pre-IP administration to end of each Experimental Session.

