- After video recording has begun, at approximately 9:00 in the morning, a qualified staff member will administer the initial dose of IMP with an electrolyte-containing fluid. The participant will sit or recline on comfortable furnishings. Eyeshades and a program of music will be provided for the participant if they wish to use them. Whenever they wish, participants may speak to the therapy pair, who will provide guidance and support, as needed.
- After the first hour, if the participant has not spoken spontaneously, the therapy pair will check in with them about the nature of the experience. For the rest of the experience, as appropriate, the therapy pair will support and encourage the participant in emotional

processing and resolution of whatever psychological material is emerging, as described in the Treatment Manual.

- Water or Electrolyte-containing fluids will be provided throughout the session but not to exceed three liters overall.
- Blood pressure, body temperature, and pulse will be measured approximately 1.5 to 2 hours after the initial dose, before the supplemental dose is administered.
- If the participant prefers not to have the supplemental dose, the therapy pair will document the reason.
- The site physician will be contacted with a brief description of how the session is progressing and the recent vital signs. The site physician will approve or deny the administration of the supplemental dose. If an AE requiring medical attention has occurred between the initial and supplemental dose, the site physician will determine whether the supplemental dose is recommended or not. If medical attention is needed, the site physician will provide further instruction or consult the Medical Monitor.
- A supplemental dose will be administered with a glass of electrolyte-containing fluid approximately 1.5 to 2 hours after the initial dose, unless tolerability issues emerge with the first dose or it is refused by the participant.
- Food will be provided during the latter part of the session.
- If there is an approved companion, that person may arrive as agreed upon but will wait in the waiting room until a member of the therapy pair brings them to the session room. Alternatively, the companion may arrive after the session has ended.

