#### *End of Experimental Session*

- The therapy pair will record AEs and concomitant medications.
- Blood pressure, body temperature, and pulse will be measured approximately 8 hours after the initial dose.
- The therapy pair will administer the C-SSRS.
- The session may be ended if all medical and psychiatric parameters are acceptable, elevations in vital signs have resolved to pre-IMP levels, the participant is alert, ambulatory, and emotionally stable, and the night attendant has arrived.
- The therapy pair or site physician shall remain available to participants via 24-hour cellular phone for support, as needed.

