7.8 Safety Analyses

Safety analyses will confirm safety data with summary tables listing exposure to IMP, unsolicited AEs, concomitant medications, suicidal ideation and behavior, and vital signs overall and by treatment received. If a participant has more than one AE mapped to the same PT, that AE will be reported once using the highest severity. AEs that occur on Day 0 (Experimental Session), Day 1, Day 2 after IMP administration will be presented separately. Comparisons will be presented of relative incidence of AEs during experimental Sessions.

Frequency and incidence of concomitant medications will be displayed by generic name, sorted by class, and summarized overall and by treatment group. Frequency and incidence of positive or serious ideation and suicidal behavior will be presented using descriptive statistics of C-SSRS scores in tabular format. Vital signs (heart rate, blood pressure, and body temperature) for Experimental Sessions will be summarized using descriptive statistics in tabular format listing values at pre-IMP administration, prior to the supplemental dose, and at the end of each Experimental Session by treatment group.

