7.8.5 Summary of Vital Signs

Vital signs (heart rate, BP, and body temperature) for Experimental Sessions will be summarized using descriptive statistics in tabular format listing values at pre-IMP, prior to the supplemental dose, and at the end of each Experimental Session.

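### Safety Objective 11 defines vital-sign change only to the end of the session, so it largely reflects recovery; no within-participant change to the near-peak pre-supplemental reading is planned

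*SAP*

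**What the plan says.** **The objective.** Protocol 2.4, item 11: "Assess mean changes in blood pressure, heart rate, and body temperature from pre-IP administration to end of each Experimental Session". SAP 2.3 carries it over with one changed abbreviation: "Assess mean changes in blood pressure, heart rate, and body temperature from pre-IMP administration to end of each Experimental Session". It is the only numbered safety objective that asks for the size of a vital-sign change.

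**The planned table.** SAP 7.8.5 gives descriptive statistics, "listing values at pre-IMP, prior to the supplemental dose, and at the end of each Experimental Session". SAP 7.8 has the same three time points: "listing values at pre-IMP administration, prior to the supplemental dose, and at the end of each Experimental Session by treatment group". Protocol 13.2.4 plans the same. None of these sections mentions a change score.

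**When readings are taken.** Protocol 7.3.1, in the text after Table 9: "Blood pressure, body temperature, and pulse will be measured approximately 1.5 to 2 hours after the initial dose, before the supplemental dose is administered". Under the end-of-session steps: "Blood pressure, body temperature, and pulse will be measured approximately 8 hours after the initial dose". Footnote F to Tables 5 and 6 puts the last reading at about 6 to 8 hours. It also keeps the middle reading when the supplemental dose is not given. Table 9 puts the last reading at 16:30 after a 9:00 dose.

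**Release from the session.** Protocol 7.3.1 allows the session to end once, among other conditions, "elevations in vital signs have resolved to pre-IMP levels".

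**Time course.** Protocol 1.2.2: "peak effects occur 1.25 to two hours after the initial dose". The same section says that effects last 5 to 8 hours when a supplemental dose is given. Protocol 9.2.2.1 expects the heart-rate and blood-pressure changes to last at most 8 hours.

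**The concern.** A change score shows an acute drug effect only if its second reading is taken while the effect is present. Objective 11 takes its second reading late, when the protocol itself expects the effect to be fading or gone. A small mean change would then show that participants had recovered by evening, and could be misread as a small effect of the drug.

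This matters more since the SAP became a safety-only plan after early termination (SAP 1.0), because SAP 2.3 says that the safety data are meant to support the package insert. The protocol also treats temperature risk as a rise from the person's own baseline: Protocol 9.2.3.1 sets action points at 1 °C and 1.5 °C above Baseline. A within-participant change near the peak is the matching summary, and neither document plans it.

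**Working it through.** **Inputs**

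| Quantity | Value, hours after initial dose | Source |
|---|---|---|
| Stated peak of effects | 1.25 to 2 | Protocol 1.2.2 |
| Duration with supplemental dose | 5 to 8 | Protocol 1.2.2 |
| Expected duration of blood-pressure and heart-rate change | at most 8 | Protocol 9.2.2.1 |
| Pre-supplemental reading | 1.5 to 2 | Protocol 7.3.1 |
| Final reading | 6 to 8; about 8; 16:30 | Tables 5 and 6 footnote F; 7.3.1; Table 9 |

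**Step 1. Reproduce the timing of the final reading.** Table 9: 16:30 − 9:00 = 7.5 h. This lies inside the 6 to 8 h of footnote F and close to the 8 h of 7.3.1, so the three statements are compatible.

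**Step 2. Gap from stated peak to final reading.** Shortest gap = earliest reading − latest peak. Longest gap = latest reading − earliest peak.

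- Footnote F: 6 − 2 = 4 h to 8 − 1.25 = 6.75 h.
- 7.3.1 text: 8 − 2 = 6 h to 8 − 1.25 = 6.75 h.
- Table 9: 7.5 − 2 = 5.5 h to 7.5 − 1.25 = 6.25 h.

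**Step 3. Final reading against duration.** A reading at 6 to 8 h falls in the later part of the 5 to 8 h range, or at its end, and reaches the 8 h limit given for blood pressure and heart rate. Some residual effect is possible at 6 h; little is expected at 8 h.

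**Step 4. Pre-supplemental reading against peak.** 1.5 ≥ 1.25 and 2 ≤ 2, so the whole 1.5 to 2 h window lies inside the stated peak window.

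**Step 5. Sensitivity to a second peak.** Assume that the supplemental dose, given at 1.5 to 2 h, has its own peak 1.25 to 2 h later. That peak falls at 1.5 + 1.25 = 2.75 h to 2 + 2 = 4 h. The gap is then 6 − 4 = 2 h to 8 − 2.75 = 5.25 h. The final reading is still after the peak.

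**Step 6. What the tabulated levels can and cannot give.** The difference between two tabulated means equals the mean change only if the same sessions supply both readings. The SD of the change is √(s₁² + s₂² − 2·r·s₁·s₂), where s₁ and s₂ are the SDs at the two readings and r is the within-participant correlation. The table gives s₁ and s₂ but not r, so the SD of the change cannot be recovered from it.

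**Step 7. Numbers available.** About 20 participants randomized 1:1 is 20 ÷ 2 = about 10 per arm. Only one arm receives Session 3, so that session has at most about 10.

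**The case against.** The strongest reply is that the near-peak reading is not lost. It is scheduled at every session, and SAP 7.8 and 7.8.5 give it the same standing as the other two. With complete readings a reader can subtract two means, and the sponsor can compute change scores later at no cost in bias or multiplicity. This stands. A reader might infer that the planned output shows only recovery or hides the acute effect. The documents do not support that: near-peak levels will be reported. The defect is in the objective's definition and in the missing change scores.

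Second, the stated peak is for MDMA effects in general after the initial dose. It is not a peak time for blood pressure, heart rate or temperature, nor for the divided dose. This also stands, and it is why the statement is that the contrast largely reflects recovery, not that it does so entirely. Step 5 shows that a later peak narrows the gap without reversing the order. Protocol 4.6 also expects the supplemental dose to add little to the physiological peak.

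Third, one might read the release rule as forcing the final change to zero, or say that the final reading is undefined. Neither follows. The protocol times the final reading by the clock, and release is a separate condition. One narrow gap remains: if a raised reading is repeated before release, neither document says which value counts as end of session. Using the release value would pull the change towards zero.

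Finally, a reader might want a figure for the precision lost. It would rest wholly on an assumed correlation and SD, and the SAP plans no confidence interval for vital signs, so none is claimed.

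**Conclusion.** The point holds, at low severity. Followed as written, the plan's one vital-sign change objective would understate the acute effect, because its second reading comes 4 to 6.75 hours after the stated general peak (2 to 5.25 hours if the supplemental dose has its own peak). A reading inside the stated peak window is already required at each session, but no within-participant change to it is planned. SAP 7.8.5 also does not say that it will produce the change Objective 11 asks for.

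The conclusion assumes that vital signs broadly follow the general time course in Protocol 1.2.2 and the duration in 9.2.2.1. The consequence is limited. The summary is descriptive, the sample is about 20 and smaller at Session 3, adverse events on Days 0 to 2 are reported separately, and nothing here biases one arm against the other.

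**What to change.** In Objective 11 and SAP 7.8.5, state that n, mean and SD of the within-participant change from pre-IMP will be reported for each session to:

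1. the pre-supplemental reading, or the reading taken when that dose would have been due if it is not given, labelled as the acute effect;
2. the scheduled 6 to 8 hour reading, labelled as recovery.

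Define the end-of-session value as the scheduled clock-time reading, not a repeat taken at release. Keep the planned tables of levels.

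The cost is a few table columns and one sentence of definition. Every reading needed is already scheduled at each session, so nothing new is collected. One limit should be noted beside the table: the first change precedes the supplemental dose, so it describes the acute effect of the initial 120 mg only.

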2.4 Exploratory Objectives

Exploratory objectives include analyses of baseline predictors of treatment outcome (e.g., adverse childhood experiences, history of mild TBI), and post-treatment changes in self report measures of clinical state, including depression, PTSD, and moral injury as assessed by:

1. Explore changes between the two treatment groups in PTSD symptom clusters of re-experiencing, avoidance, negative alterations in cognition and mood, and hyperarousal, as measured by changes in CAPS-5 subscale scores from Baseline to Post-treatment and Follow-up.
2. Explore trajectories of change and onset of treatment effectiveness within and between groups using multiple assessments with PCL-5 self-reports.
3. Explore the effect of adverse childhood experiences (ACE) on the CAPS-5 Total Severity analyses.
4. Explore differences between treatment groups using measures below regarding changes in clinical state associated with MDMA treatment, and regarding baseline predictors of outcome using the following measures:
 - a. Acceptance and Action Questionnaire (AAQ-II)
 - b. Dissociative Subtype of PTSD Interview (DSP-I)
 - c. Columbia Suicide Severity Rating Scale (C-SSRS)
 - d. Self Compassion Scale (SCS)
 - e. Buss-Perry Aggression Questionnaire-Short Form (BPAQ-SF)
 - f. Deployment Risk and Resilience Inventory 2 (DRRI-2)
 - g. Life Events Checklist (LEC-5)
 - h. PTSD Checklist for DSM-5 (PCL-5)
 - i. Moral Injury (MIES)
 - j. Depression (BDI-II)
 - k. Posttraumatic Growth Inventory (PTGI)
 - l. Chronic Pain Grade Scale (CPGS)
 - m. World Health Organization Quality of Life-Brief Form (WHOQOL-BREF)
 - n. Ohio State University Traumatic Brain Injury (OSU-TBI)
 - o. The Utilization of Facility and Emergent Care (UFEC)
 - p. Addictive behaviors including Alcohol Use Disorders Identification Test (AUDIT), Drug Use Disorders Identification Test (DUDIT)

